1

2

### 3 PROTOCOL SYNOPSIS

Protocol Title	Initialization and Adaptation of Insulin Delivery Settings to Improve Clinical Outcomes with AID Use
Device	1) t:slim X2 insulin pump with Control-IQ technology (Control-IQ System) 2) An automatic settings initializer and adaptation system running on the server
Type of Study	Prospective, Single Arm, Single Center Feasibility Study
Rational	The purpose of this study is to obtain preliminary safety and performance data on a settings initialization and adaptation algorithm used in conjunction with closed-loop control. Based on data from simulations and current system use, an algorithm to more accurately initialize settings and adapt them over time, faster than typical HCP visits, would benefit users onboarding from multiple daily injections (MDI) and help them reach optimal glycemic outcomes faster. Outcomes of this study will allow for the determination of an optimal product configuration for adaptive settings and the ability to clinically test a commercial version of the new product for effectiveness.
Objectives	Primary objective: To demonstrate the safety of the system, by assessing the number of severe hypoglycemic events (needing assistance) compared to expected incidence  Secondary objective: Compare time in range metrics and adverse events in the full 24 hour period, overnight and during the day, after each week of settings adaptation. The number of physician overrides/physician initiated changes in pump settings will also be tracked.
Primary Endpoints	1) Primary Endpoint: a. To demonstrate the safety of the system, by assessing the number of severe hypoglycemic events (needing assistance) compared to expected incidence 2) Secondary Endpoints: a. Time in range 70-180 mg/dL b. Time < 54 mg/dL c. Time < 70 mg/dL d. Time > 180 mg/dL e. Time > 250 mg/dL f. Time in tight glycemic range 70-140 mg/dL g. Post-prandial glycemic peak h. 4-hour post meal glucose AUC i. Sensor glucose median and interquartile range j. CGM metrics daytime vs. nighttime k. CGM metrics compared each week after adaptation l. DKA

---

Confidential

Contains trade secrets and/or confidential information exempt from disclosure from 21 CFR 20.61

	
 
m. Adverse Device Effects
 
n. Serious Adverse Events
 
o. Change in total daily insulin use, basal and bolus
 
p. Number of physician overrides/physician initiated changes in pump settings
 
q. Patient Reported Outcomes
 

Duration of Study	Up to 17 weeks total, to allow for 2 to 4 weeks of CGM run-in if needed, then 13 weeks of pump/AID use with weekly settings adaptation
Study Design	
Adults (age <math>\geq</math> 18 years of age) with type 1 diabetes, who are using multiple daily injections, will be required to collect baseline CGM data for the first 2 weeks if not already Dexcom G6 users with at least 11 of 14 days of CGM use for the 14 days prior to enrollment. They may repeat this 14 day run-in period if adequate CGM data is not collected, or study staff feel it is necessary to continue to monitor their insulin dose.
 
Subjects will then proceed to pump/Control-IQ training, where an algorithm performed on a paper worksheet will be used to recommend initial basal rate, carbohydrate ratio and correction factor settings.
 
Subjects will then wear the insulin pump with Control-IQ technology active for 13 weeks, and at day 3 and at the end of each week will:
 
 
1) Upload their pump using the USB uploader
 
2) Have their study physician review the settings recommendations on the pump download report that will appear after each download.
 
3) Change their settings after being called by the study physician to match the new recommendations.
 
4) Upload their pump again so the study physician can verify the settings have been changed appropriately, and verify the correct settings have been applied to the correct pump assigned to the subject by verifying the serial number on the recommendations report to the changes in t:connect.
 
5) Physicians can at any time adjust pump settings and override the settings adaptation recommendations for safety concerns, and convert scheduled phone follow-up visits to in clinic visit at their discretion.
 
 
A semi-structured one-on-one interview may be completed concurrent with the 13-Week Visit or within a 28-day period following that visit. The interview will last approximately 30 minutes and will be conducted by Tandem staff using a script of open-ended questions to gather feedback and reactions to the

---

Confidential

Contains trade secrets and/or confidential information exempt from disclosure from 21 CFR 20.61

	automated initialization and adaptation system, as well as the use of Closed-Loop Control.
Study Population	Male and female subjects $\geq$ 18 years of age with type 1 diabetes, who are current MDI users, who have a baseline A1c at screening between 7.5 to 11%
Number of Subjects	Up to 45 subjects may sign the consent form and be screened, with the goal that 30 subjects start use of the study device, and at least 20 subjects complete the trial.
Number of Sites	1 clinical site in the United States
Main Criteria for Inclusion	
Eligibility to enroll in the study will be assessed based on the following inclusion criteria:
 
 
1. Adult subjects <math>\geq</math> age 18 years
 
2. Clinical diagnosis of type 1 diabetes for at least one year
 
3. Using a basal/bolus regimen by injection (MDI therapy)
 
4. Total daily dose <math>\geq</math> 10 units/day
 
5. Willing to use only aspart (novolog) or lispro (humalog) U-100 insulin with the study pump.
 
6. A1c <math>\geq</math> 7.5% and <math>\leq</math> 11% at screening
 
7. Not pregnant or planning a pregnancy during the time period of the study.
 
8. Has current glucagon product to treat severe hypoglycemia (injectable or nasal) at home (will provide prescription if they do not have one)
 
9. Willingness to follow study procedures and a signed informed consent form
 

Main Criteria for Exclusion	
Eligibility to enroll in the study will be assessed based on the following exclusion criteria:
 
 
1. Two or more episodes of severe hypoglycemia (needing assistance) in the past 6 months
 
2. Two or more episodes of diabetic ketoacidosis in the past 6 months
 
3. Inpatient psychiatric treatment in the past 6 months
 
4. History of drug abuse (defined as any illicit drug use) or history of alcohol abuse prior to screening or unwillingness to agree to abstain from illicit drugs throughout the study
 
5. Significant chronic kidney disease or hemodialysis
 
6. Significant liver disease
 
7. History of adrenal insufficiency
 
8. History of abnormal TSH consistent with hypothyroidism or hyperthyroidism that is not appropriately treated
 
9. Other chronic disease/condition determined by investigator to interfere with participation in the study
 
10. Use of glucocorticoids, beta blockers or other medications determined by investigator to interfere with study
 

Confidential

Contains trade secrets and/or confidential information exempt from disclosure from 21 CFR 20.61

	
11. Use of long-acting insulin, inhaled insulin (Afrezza), or use of any non-insulin glucose lowering agents (i.e. SGLT-2 inhibitor) other than Metformin with the study pump
 
12. Subject is pregnant or lactating or intending to become pregnant before or during participation in this study.
 
13. Investigator judgement that subject would not be able to complete the trial.

Procedures in Screening/Baseline Period	At screening, baseline data will be collected. For Dexcom G6 users, mean/median sensor glucose, TIR and all glycemic outcomes will be recorded as baseline data if data is available for the at least 11 of the last 14 days. Those without adequate baseline data will collect Dexcom G6 sensor data to establish a baseline over the next 2 weeks.
Management of Adverse Events	Safety information will be collected weekly during study clinic phone calls, or more frequently if a severe AE occurs. The event, date of onset, severity, seriousness, duration and relationship to the device/adaptation system will be documented. All reported device-related AEs will be followed until they are adequately resolved or stabilized, or until study completion/termination, whichever comes first.
Statistical Analysis	Descriptive statistics will be used to evaluate rates of AEs as well as glycemic outcomes over time as the algorithm adapts insulin delivery settings.

122

123 The study will be conducted and documented in accordance with the IRB, FDA, ICH and GCP  
 124 guidelines.

125

126

---

Confidential

*Contains trade secrets and/or confidential information exempt from disclosure from 21 CFR 20.61*

127 **4 BACKGROUND**

128 **4.1 DISEASE BACKGROUND**

129 Type 1 diabetes affects 1.25 million people in the United States. Approximately 70% of  
130 individuals with type 1 diabetes report poor metabolic control, and do not meet the American  
131 Diabetes Association's recommended goal of hemoglobin A1c (HbA1c) level of 7.0% for children  
132 and adults. These findings indicate the need for better approaches to type 1 diabetes  
133 management.

134 Recent estimates suggest that approximately 400,000 U.S. patients with type 1 diabetes (T1D)  
135 use insulin pumps. Adoption of pump therapy varies by geography and may be related to  
136 healthcare provider preference or patient characteristics and socioeconomic status. Use of insulin  
137 pumps is more common in individuals of higher socioeconomic status as reflected by  
138 race/ethnicity, private health insurance, family income, and education. Additionally, referrals  
139 from healthcare providers and insurance approvals are critical determinants for who becomes a  
140 pump user in the United States.

141 However, a main barrier to starting pump therapy and staying on it is having to enter insulin  
142 delivery settings into the pump (ie basal rate, carbohydrate ratio, correction factor) and  
143 optimizing those settings for each individual. In this trial, we will test the safety and feasibility of  
144 using a settings initializer for individuals onboarding to the t:slim X2 pump with Control-IQ  
145 technology, with weekly adaptations of insulin delivery settings over ~13 weeks.

146 **4.2 DEVICE BACKGROUND**

147 The t:slim X2 insulin pump with Control-IQ technology is an advanced hybrid closed-loop  
148 (HCL) system, developed and manufactured by Tandem Diabetes Care, Inc. and cleared in the  
149 U.S. by the FDA for individuals with type 1 diabetes. Control-IQ is integrated with the Dexcom  
150 G6 continuous glucose monitor (CGM) and uses CGM values to predict glucose values 30  
151 minutes in the future. Based on the predicted glucose, Control-IQ modulates basal insulin  
152 delivery, and delivers automated correction boluses to mitigate impending hyperglycemia. The  
153 current Control-IQ system is FDA approved down to age 6 years old for individuals with type 1  
154 diabetes, and has been found to improve time in range (70-180 mg/dL) and decrease both time <  
155 70 mg/dL and time >180 mg/dL (1,2).

156 **4.3 SETTINGS OPTIMIZER**

157 For this study, insulin delivery settings initialization will use a paper worksheet (Figure 1) to  
158 guide initial settings.

159

160

---

Confidential

*Contains trade secrets and/or confidential information exempt from disclosure from 21 CFR 20.61*

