182 **Primary objective:** To demonstrate the safety of the settings initialization and adaptation  
183 algorithm when in conjunction with Control-IQ technology, by assessing the number of severe  
184 hypoglycemic events (needing assistance) compared to expected incidence

185 **Secondary objective:** Compare time in range metrics and adverse events in the full 24 hour period,  
186 overnight and during the day, after each week of settings adaptation. The number of physician  
187 overrides/physician initiated changes in pump settings will also be tracked.

188 **5.2 STUDY DESIGN**

189 This feasibility study is a prospective, single arm study, evaluating an algorithm to recommend  
190 insulin pump settings at pump start (initialization) and then adjust settings at 3 days, at 7 days,  
191 and then weekly through 13 weeks.

192 Adults (age  $\geq$  18 years of age) with type 1 diabetes, who are using multiple daily injections, will  
193 be required to collect baseline CGM data for the first 2 weeks if not already Dexcom G6 users  
194 with at least 11 of 14 days of CGM use for the 14 days prior to enrollment. They may repeat this  
195 14 day run-in period if adequate CGM data is not collected, or study staff feel it is necessary to  
196 continue to monitor their insulin dose.

197 Up to 45 subjects may sign the consent form and be screened, with the goal that up to 30 subjects  
198 start use of the study device, and at least 20 subjects complete the trial.

199 Enrollment goals for baseline A1c at screening are:

200     • At least 5 subjects with A1c 8% - 8.9%  
201     • At least 5 subjects with A1c  $\geq$  9%

202 Subjects will then proceed to pump/Control-IQ training, where an algorithm based worksheet  
203 will be used to recommend initial basal rate, carbohydrate ratio and correction factor settings.

205 Subjects will then wear the insulin pump with Control-IQ technology active, and at 3 days after  
206 training, 7 days after training, and then every 7 days will:

207     1) Upload their pump using the USB uploader  
208     2) Have their study physician review the settings recommendations on the pump download  
209        report that will appear after each download.  
210     3) Change their settings after being called by the study physician to match the new  
211        recommendations.  
212     4) Upload their pump again so the study physician can verify the settings have been changed  

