### 226 **5.3 STUDY ENDPOINTS**

227 1) Primary Endpoint:

- 228 a. To demonstrate the safety of the system, by assessing the number of severe  
229 hypoglycemic events (needing assistance) compared to expected incidence

230 2) Secondary Endpoints:

- 231 a. Time in range 70-180 mg/dL
- 232 b. Time < 54 mg/dL
- 233 c. Time < 70 mg/dL
- 234 d. Time > 180 mg/dL
- 235 e. Time > 250 mg/dL
- 236 f. Time in tight glycemic range 70-140 mg/dL
- 237 g. Post-prandial glycemic peak
- 238 h. 4-hour post meal glucose AUC
- 239 i. Sensor glucose median and interquartile range
- 240 j. CGM metrics daytime vs. nighttime
- 241 k. CGM metrics compared each week after adaptation
- 242 l. DKA
- 243 m. Serious Adverse Events
- 244 n. Adverse Device Effects
- 245 o. Change in total daily insulin use, basal and bolus
- 246 p. Number of physician overrides/physician initiated changes in pump settings
- 247 q. Patient Reported Outcomes

248 **6 SUBJECT SELECTION**

249 **6.1 SUBJECT POPULATION**

250 **6.1.1 INCLUSION CRITERIA:**

251 Eligibility to enroll in the study will be assessed based on the following inclusion criteria:

- 252 1) Adult subjects  $\geq$  age 18 years
- 253 2) Clinical diagnosis of type 1 diabetes for at least one year
- 254 3) Using a basal/bolus regimen by injection (MDI therapy)
- 255 4) Total daily dose  $\geq$  10 units/day
- 256 5) Willing to use only aspart (novolog) or lispro (humalog) U-100 insulin with the study  
257 pump.
- 258 6) A1c  $\geq$  7.5% and  $\leq$  11% at screening
- 259 7) Not pregnant or planning a pregnancy during the time period of the study.
- 260 8) Has current glucagon product to treat severe hypoglycemia (injectable or nasal) at home  
261 (will provide prescription if they do not have one)
- 262 9) Willingness to follow study procedures and a signed informed consent form

263 **6.1.2 EXCLUSION CRITERIA:**

264 Eligibility to enroll in the study will be assessed based on the following exclusion criteria:

- 265 1) Two or more episodes of severe hypoglycemia (needing assistance) in the past 6 months
- 266 2) Two or more episodes of diabetic ketoacidosis in the past 6 months
- 267 3) Inpatient psychiatric treatment in the past 6 months
- 268 4) History of drug abuse (defined as any illicit drug use) or history of alcohol abuse prior to  
269 screening or unwillingness to agree to abstain from illicit drugs throughout the study
- 270 5) Significant chronic kidney disease or hemodialysis
- 271 6) Significant liver disease

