## 409 **7.8 POST STUDY PHONE CALL**

410 All participants will have a post-study phone call 3 ( $\pm 1$ ) days after the date of their final visit and  
411 transition back to their prior insulin therapy, during which the following will occur:

412 • Check on transition back to usual home diabetes care

413 • Assessment of adverse events

414

---

Confidential

Contains trade secrets and/or confidential information exempt from disclosure from 21 CFR 20.61

415 **8 STATISTICAL CONSIDERATIONS**

416 **8.1 STATISTICAL ANALYSIS:**

417 This feasibility study is a prospective, single arm study, evaluating al algorithm to recommend  
418 insulin pump settings at pump start (initialization) and then weekly for 13 weeks.

419 Descriptive statistics of the rates of severe hypoglycemia, DKA, and serious adverse events will  
420 be reported for baseline (with CGM run-in data) and compared to changes after each weekly  
421 adaptation. Additionally, descriptive statistics of glycemic outcomes will for baseline and each  
422 intervention configuration will be provided.

423 The statistics will include all primary and secondary outcomes of the study as listed in section  
424 5.3. These statistics will be calculated at the patient-level, and a sub-analysis of daytime vs.  
425 nighttime statistics will be provided.

426

427

428 **9 RISKS AND BENEFITS**

429 **9.1 POTENTIAL RISKS AND BENEFITS OF THE DEVICE**

430 Risks and Benefits are detailed below. Loss of confidentiality is a potential risk; however, data  
431 are handled to minimize this risk. Hypoglycemia, hyperglycemia and ketone formation are  
432 always a risk in participants with diabetes and participants will be monitored for this.

433 **9.2 VENIPUNCTURE RISKS**

434 A hollow needle/plastic tube may be placed in the arm for taking blood samples. Blood draws  
435 can cause some common reactions like pain, bruising, or redness at the sampling site. Less  
436 common reactions include bleeding from the sampling site, formation of a small blood clot or  
437 swelling of the vein and surrounding tissues, and fainting.

438 **9.3 FINGERSTICK RISKS**

439 About 1 drop of blood will be removed by fingerstick for measuring blood glucose and  
440 sometimes Hemoglobin A1c (HbA1c) or other tests. This is a standard method used to obtain  
441 blood for routine hospital laboratory tests. Pain is common at the time of lancing. In about 1 in  

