442 10 cases, a small amount of bleeding under the skin will produce a bruise. A small scar may  
443 persist for several weeks. The risk of local infection is less than 1 in 1000. This should not be a  
444 significant contributor to risks in this study as fingersticks are part of the usual care for people  
445 with diabetes.

446 **9.4 SUBCUTANEOUS CATHETER RISKS (CGM)**

447 With CGM use participants are at low risk for developing a local skin infection at the site of the  
448 sensor needle placement. If a catheter is left under the skin for more than 24 hours, it is possible  
449 to get an infection where it goes into the skin, with swelling, redness and pain. There may be  
450 bleeding where the catheter is put in and bleeding under the skin causes a bruise (1 in 10 risk).

451 On rare occasions, the CGM may break and leave a small portion of the sensor probe under the  
452 skin that may cause redness, swelling or pain at the insertion site. The participant will be  
453 instructed to notify the study coordinator immediately if this occurs.

454 **9.5 RISK OF HYPOGLYCEMIA**

455 As with any person having diabetes and using insulin, there is always a risk of having a low  
456 blood sugar (hypoglycemia). The frequency of hypoglycemia should be no more and possibly  
457 less than it would be as part of daily living. Symptoms of hypoglycemia can include sweating,  
458 jitteriness, and not feeling well. Just as at home, there is the possibility of fainting or seizures  
459 (convulsions) and that for a few days the participant may not be as aware of symptoms of  
460 hypoglycemia. A CGM functioning poorly and significantly over-reading glucose values could  
461 lead to inappropriate insulin delivery.

462            **9.6 RISK OF HYPERGLYCEMIA**

463            Hyperglycemia and ketonemia could occur if insulin delivery is attenuated or suspended for an  
464            extended period or if the pump or infusion set is not working properly. A CGM functioning  
465            poorly and significantly under-reading glucose values could lead to inappropriate suspension of  
466            insulin delivery. All subjects will be issued a glucose meter and glucose test strips, and a ketone  
467            meter and ketone strips to use to carefully monitor for hyperglycemia and be given instructions  
468            on how to mitigate hyperglycemia should it occur.

469            **9.7 RISK OF DEVICE REUSE**

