## 761 **11.12 PARTICIPANT DISCONTINUATION OF STUDY DEVICE**

762 Rules for discontinuing study device use are described below.

- 763 1) The investigator believes it is unsafe for the participant to continue on the intervention.  
*764 This could be due to the development of a new medical condition or worsening of an  
765 existing condition; or participant behavior contrary to the indications for use of the  
766 device that imposes on the participant's safety*
- 767 2) The participant requests that the treatment be stopped
- 768 3) Participant pregnancy  
*769 If pregnancy occurs, the participant will be discontinued from the study entirely.  
770 Otherwise, even if the study device system is discontinued, the participant will be  
771 encouraged to remain in the study through the final study visit.*
- 772 4) Two distinct episodes of DKA as defined in section 11.4
- 773 5) Two distinct episodes of severe hypoglycemia as defined in section 11.3
- 774 6) The investigator may have a subject temporarily stop use of Control-IQ during: periods  
775 of significant illness, temperature >101.5, use of oral or injectable glucocorticoids, use of  
776 epinephrine for the emergency treatment of a severe allergic reaction or asthma attack, or  
777 if a subject is going to the hospital for any reason. If the investigator believes the period of  
778 illness may be prolonged or put the safety of the subject or the overall study at risk, the  
779 investigator may withdraw the subject from the study.

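### The primary endpoint promises to demonstrate safety against an expected incidence of severe hypoglycemia that is never given a value, source or criterion, and the planned exposure supports only a rough estimate of the rate.

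*Combined protocol and SAP*

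**What the plan says.** The synopsis gives the primary endpoint as "To demonstrate the safety of the system, by assessing the number of severe hypoglycemic events (needing assistance) compared to expected incidence". Section 5.3 opens its primary endpoint the same way ("To demonstrate the safety of the system, by assessing the number of severe"), and the primary objective in 5.1 ends on the same comparator: "hypoglycemic events (needing assistance) compared to expected incidence".

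On analysis, the synopsis says only: "Descriptive statistics will be used to evaluate rates of AEs as well as glycemic outcomes over time". Section 8.1 says that rates of severe hypoglycemia, DKA and serious adverse events will "be reported for baseline (with CGM run-in data) and compared to changes after each weekly" adaptation. It adds: "The statistics will include all primary and secondary outcomes of the study as listed in section" 5.3. The primary event count is therefore covered, but descriptively.

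Three other places bear on severe hypoglycemia:

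- Section 9.5 offers an expectation about hypoglycemia in general, relative to daily living: "The frequency of hypoglycemia should be no more and possibly" less. It gives no rate.
- Section 11.12 lists among the reasons for stopping the device: "Two distinct episodes of severe hypoglycemia as defined in section 11.3". The plan thus foresees repeat events in one person.
- Section 11.13 names three or more cases across the study as a ground for suspending or stopping it.

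The rationale in the synopsis describes the study's purpose as preliminary safety and performance data.

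**The concern.** A comparison needs something to compare with. The sole primary endpoint names an expected incidence, but the documents do not say what it is, where it comes from, over what time base it runs, or what result would count as acceptable. Without that, the comparison cannot be carried out, and a reference could be chosen once the number of events is known.

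The wording also claims more than the study can deliver. To demonstrate safety is to rule out an unacceptable rate. A single-arm study of this size, with descriptive analysis and no interval specified, can only estimate the rate loosely. At stake is the conclusion drawn from the primary endpoint: a report of zero or few events could be presented as safety shown, when the data would be compatible with a wide range of rates.

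**Working it through.** **Is the comparator defined anywhere?**

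| Place | What it gives | Does it supply the expected incidence? |
|---|---|---|
| Synopsis, 5.1, 5.3 | The term only | No value, source or criterion |
| 9.5 | A qualitative expectation about hypoglycemia generally | No rate, and not specific to severe events |
| 11.13 | Three or more cases | A suspend/stop count; no person-time, no link to an expected rate, and fewer than three is not called success |
| 8.1 | Run-in against each adaptation week | A different comparator |

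The protocol states no sample-size calculation, margin or confidence level, so there is no figure of its own to reproduce.

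**Exposure.** Inputs: 30 subjects starting and at least 20 completing (synopsis, Number of Subjects; 5.2 says up to 30); 13 weeks on the device (synopsis, Duration); final visit window of 7 days either way (7.4); run-in of 2 to 4 weeks if needed (synopsis). Person-years = subjects × weeks / 52.

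- On device: 20 × 13/52 = 5.0; 30 × 13/52 = 7.5.
- Extremes of the window: 20 × 12/52 = 4.6; 30 × 14/52 = 8.1.
- One adaptation week: 20/52 = 0.38; 30/52 = 0.58.
- Run-in, if every subject does it: from 20 × 2/52 = 0.77 to 30 × 4/52 = 2.3. It is less when qualifying G6 users skip the run-in.

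**What zero events would show.** The 95% level is my choice, because the documents give none. The exact Poisson upper limit with zero events is −ln(0.025)/person-years (two-sided 95%) or −ln(0.05)/person-years (one-sided 95%).

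| Exposure | Two-sided 95% upper limit | One-sided 95% upper limit |
|---|---|---|
| 5.0 person-years | 3.689/5.0 = 0.74 | 2.996/5.0 = 0.60 |
| 7.5 person-years | 3.689/7.5 = 0.49 | 2.996/7.5 = 0.40 |

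At the window extremes the two-sided limits are 3.689/4.615 = 0.80 and 3.689/8.077 = 0.46.

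**Two events**, the most that stays below the count in 11.13: the exact two-sided 95% interval is 0.05 to 1.44 per person-year at 5.0 person-years, and 0.03 to 0.96 at 7.5.

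**By participant.** With no participant affected, the exact binomial two-sided upper limit is 1 − 0.025^(1/n): 16.8% for 0 of 20 and 11.6% for 0 of 30, over 13 weeks.

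**Clustering.** The Poisson limits assume independent events. If underlying rates differ between people with gamma variance v (an assumption), the zero-event limit becomes (0.025^(−v/n) − 1)/(0.25v). With v = 1 it is 0.81 (n = 20) or 0.52 (n = 30); with v = 5 it is 1.21 or 0.68. Clustering therefore raises the limits.

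**The case against.** The strongest reply is that this is a feasibility study. It is single-arm and single-centre, it plans descriptive statistics only, it makes no formal test, and it precedes a later clinical test of a commercial version. Wide intervals come with 20 to 30 subjects and are not in themselves a fault. Participants' protection does not rest on the missing rate either: 11.12 to 11.14 set individual discontinuation rules, a study-level count and sponsor medical review. All of this stands. It removes any case for more subjects or a hypothesis test, and it lowers the severity. It does not supply the comparator, and it counts against the wording, since a study whose rationale is preliminary safety data should not claim to demonstrate safety.

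A second reply is that 8.1 covers every outcome in 5.3, so the primary endpoint is not left unanalysed. That is right as far as description goes, but describing a count does not compare it with an unstated incidence.

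A reader might also infer that the weekly comparison in 8.1 would usually set zero against zero, or would often suggest a false rise after run-in. The documents do not support either statement. Both depend on an event rate that the protocol does not give, and 8.1 attaches no decision to any weekly pattern. What can be said is that the comparison is a different one and that its exposure is small.

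**Conclusion.** The point holds. The primary comparison cannot be made as written, because the expected incidence has no value, source or criterion, and the run-in comparison in 8.1 does not replace it. With about 13 weeks each from 20 to 30 subjects, zero severe hypoglycemic events would leave a two-sided 95% upper limit of about 0.74 to 0.49 per person-year. This supports estimation, not a demonstration of safety.

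The limits need no assumed event rate, but they do assume independent events and near-complete follow-up. The subject numbers are goals. Subjects who withdraw add some exposure above the 20-completer figure, 7.5 person-years needs all 30 to finish, and an early stop under 11.13 would reduce exposure.

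A reader might go further and infer that the system is unsafe, that participants are unprotected, or that the study is too small to run. Nothing here shows that. The defect is one undefined comparator and one verb too strong for a descriptive plan. It should be fixed, but it does not invalidate the study.

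**What to change.** 1. In the synopsis, 5.1 and 5.3, restate the primary objective and endpoint as estimating the severe hypoglycemia rate to obtain preliminary safety data. State that zero events would give a two-sided 95% upper limit of about 0.49 to 0.74 per person-year, and that this assumes independent events.
2. In 8.1, define the primary analysis as one pooled on-device rate (events over person-time) with an exact Poisson two-sided 95% interval. Add the number of participants with at least one event, with an exact binomial two-sided 95% interval, because repeat events in one person are possible. Keep the weekly tabulation as descriptive.
3. If the sponsor keeps the comparison with an expected incidence, fix one sourced value before outcome data are seen, matched to the definition in 11.3 and to the severe hypoglycemia exclusion criterion. Report the pooled interval beside it. State that, at two-sided 95%, even zero events could not show a rate below any reference under about 0.49 (30 full completers) to 0.74 (20) per person-year.

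No change to 11.13 or to any clinical rule is proposed. The cost is wording plus two intervals, with no new data, visits or subjects. The downside is a less favourable stated claim, and the work of finding a matching source if a reference is kept.
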